Ciprofloxacin and Ciprofloxacin plus Fluocinolone acetonide otic solution are medications of proven efficacy and safety for the treatment of bacterial otitis externa.

In the CIFLOT III/00-01 study, Ciprofloxacin 0.3% plus Fluocinolone acetonide 0.025% (CIPRO+FLUO) vs Ciprofloxacin 0.3% (CIPRO) conducted by the Sponsor, both products were considered to have a favorable safety profile. One non-treatment-related serious adverse event (SAE; mild perichondritis) was reported in 1 subject in the CIPRO+FLUO group. In addition, 7 AEs were reported in 7 subjects (1.2%): 2 (1.0%) in the CIPRO+FLUO group and 5 (1.7%) in the CIPRO group. Both non-serious events reported in the CIPRO+FLUO group (tympanic membrane perforation) were mild in severity and were not related to study treatment. Among the 5 AEs reported in the CIPRO group, 2 were considered to be related to study treatment (mild skin eczema in the ear and mild dizziness) and 3 were not related (mild dyspepsia, moderate laryngeal edema, and moderate vertigo). No treatment-related SAEs were reported during this study.

Fluocinolone acetonide is a low to medium potency corticosteroid according to FDA classification. There is evidence that corticosteroids improve otorrhea outcomes in children and AOM in animal models, and reduce the formation of granulation tissue.

Fluocinolone acetonide is a well-known compound that is frequently used as a cream, gel, lotion, ointment for skin topical administration, and as an intravitreal implant or as an oil in ear drops. In these different topical routes of administration, plasma concentrations or pharmacokinetics of the compound could not be reported because the systemic exposure to the product was negligible. As a product administered topically into the ear, at or near the intended site of action, systemic absorption of Fluocinolone acetonide is expected to be negligible. This was confirmed by the pharmacokinetics results obtained in the SALVAT clinical studies CIFLOTIII/10IA02 and CIFLOTIII/10IA04.

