#### 7.2.1.2.1 *Serious Adverse Event*

International Conference on Harmonization (ICH) Guidelines and federal regulations define a serious adverse event (SAE) as any untoward medical occurrence that at any dose:

- Results in death;
- Is life-threatening. This means that the patient is at risk of death at the time of the event; it does not mean that the event hypothetically might have caused death if it were more severe;
- Requires or prolongs patient hospitalization;
- Results in persistent or significant disability or incapacity; or

- Is a congenital anomaly or birth defect.

Important medical events that may not be immediately life-threatening or result in death or hospitalization but that may jeopardize the patient or require intervention to prevent one of the above outcomes usually should also be considered serious.

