#### 7.2.1.2.2 Severity

The severity of each AE must be assessed and recorded on the Adverse Events page of the EDC as mild, moderate, or severe.

- Mild: An AE that does not interfere with usual activities;
- Moderate: An AE that interferes with usual activities; or
- Severe: An AE that is intense or debilitating and interferes with usual activities.

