#### 7.2.1.3 Recording Adverse Events

All AEs that occur during the study must be recorded in the Adverse Events page of the EDC. All Adverse Event EDC entries should contain a brief description of the event, date and time of onset, duration, intensity, treatment required, relationship to study medication, action taken with regard to study medication, outcome, and whether the event is classified as serious.

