- If the year is missing, the AE will be considered as ongoing and no imputation of the date will occur.

2. Patients will be classified as having withdrawn from the study due to an AE if the patient had a study drug action taken recorded as "permanently discontinued" on the Adverse Events page of the eCRF or patient had the study completion item recorded as 'No' with 'Adverse Event' as the primary reason for discontinuation on the study completion page of the eCRF.

3. AEs that occur before the first dose of study treatment will not be reported/summarized but will be listed as non-TEAE.
4. If a patient experiences more than one AE in a particular SOC, they will only be included once in the count for the SOC but will appear in the count for each appropriate PT within the SOC (unless it is the same PT).
5. AEs related to study drug tables will include only those AEs with a relationship to study drug of 'related', 'probable', 'possible', or if there is a missing relationship on the AE page of the eCRF.
6. For AE causality, when there is more than one AE of the same PT, the most related will be considered in the summary tables by causality.
7. For AE severity, when there is more than one AE of the same PT, the worst severity will be considered in the summary tables by severity.
8. If severity is missing, the event will be considered serious.

The AEs will be ordered by decreasing frequency, then alphabetically, for total patients for each SOC and PT within an SOC.

TEAEs will also be summarized by age group.

An overall summary of AEs will be provided by treatment group and overall. The summary will include incidences for the following:

- Any TEAE
- Any Treatment Related TEAE
- Any SAE
- Any Treatment Related SAE
- Any TEAE leading to Study Discontinuation
- Any TEAE leading to Permanent Study Medication Discontinuation
- Any TEAE resulting in death
- Severe TEAE
- Severe related TEAE

A by-patient listing of all adverse events (including non-treatment-emergent events) will be provided. This listing will be presented by treatment group and will include: center, patient identifier, age, sex, race, AE (SOC, PT, and verbatim term), date of onset, date of resolution, duration, severity, seriousness, seriousness criteria, action taken, outcome and causality.

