4.8.3 Deaths, Serious Adverse Events, and Other Significant Adverse Events

An overview of AEs, including the number and percentage of patients who died, reported SAEs, and discontinued due to AEs will be provided. The incidence of treatment emergent SAEs will be presented by SOC, PT, and treatment group.

Listings of all SAEs and deaths as well as AEs leading to discontinuation will be provided.

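### SAP 4.8.2 item 8 treats an adverse event with missing severity as serious, apparently in error for severe; programmed literally, it would put non-serious events in the SAE tables

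*SAP*

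**What the plan says.** SAP 4.8.2, General Rules for Adverse Events, item 8: "If severity is missing, the event will be considered serious".

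The protocol defines the two attributes in separate sections.

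- **Severity**, Protocol 7.2.1.2.2: "The severity of each AE must be assessed and recorded on the Adverse Events page of the EDC as mild, moderate, or severe". These are the only three levels.
- **Seriousness**, Protocol 7.2.1.2.1: the ICH guidelines and federal regulations "define a serious adverse event (SAE) as any untoward medical occurrence that at any dose" leads to one of a list of outcomes (death, threat to life, hospitalization, disability, congenital anomaly). Important medical events usually count as well.
- **Recording**, Protocol 7.2.1.3: each entry carries the intensity and, as a further item, "outcome, and whether the event is classified as serious".

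The SAP keeps the same separation in its outputs. The by-patient listing in 4.8.2 includes "duration, severity, seriousness, seriousness criteria, action taken, outcome and causality". The overall summary in the same section has one row for any SAE and another for severe TEAEs. SAP 4.8.3 adds: "The incidence of treatment emergent SAEs will be presented by SOC, PT, and treatment group".

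**The concern.** A missing-data rule should fill a gap on the scale where the gap occurs. Item 8 starts from a blank severity and ends with a value of seriousness. Seriousness is not a level of severity, and a blank severity field is not one of the protocol's seriousness criteria.

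The SAE tables are at stake, and they are among the first safety results a regulator reads. An event that the investigator recorded as non-serious could appear there only because another field was empty. The severity tables, which the rule was presumably meant to complete, would still lack a value for that event.

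**Working it through.** The rule has no sample size, power or error rate behind it, so the check is mainly a reading of the texts side by side.

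**1. Are the two attributes distinct in the documents?** Yes. Severity grades how far the event interferes with usual activities (Protocol 7.2.1.2.2). Seriousness depends on outcome (Protocol 7.2.1.2.1). The protocol's own background gives an event that is serious and also mild. In the earlier otitis externa trial (Protocol 2.3), "One non-treatment-related serious adverse event (SAE; mild perichondritis) was reported in 1 subject in the CIPRO+FLUO group". The eCRF is not among the documents, so separate fields are inferred from Protocol 7.2.1.3 and from the listing items in SAP 4.8.2.

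**2. What was probably intended?** Item 7, just before, deals with the severity tables. Item 5 deals with missing causality by taking the worst case on the causality scale itself: an event counts as related when the recorded relationship says so, "or if there is a missing relationship on the AE page of the eCRF". The same approach to severity gives *severe*.

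**3. Is the sentence corrected elsewhere?** No. Protocol 10.1.11 and SAP 4.8.2 to 4.8.3 give no other rule for missing severity. SAP 4.2 places programming specifications in a table-shell document that is not available here.

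**4. What happens to one treatment-emergent, non-serious event with blank severity?**

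| Output | Item 8 as written | Item 8 with *severe* |
|---|---|---|
| Any-SAE row; SAEs by SOC and PT | counted | not counted |
| Related-SAE rows, if relationship is also blank (item 5) | counted | not counted |
| Severe-TEAE row; tables by severity | no category | counted as severe |
| Seriousness criterion on record | none | none needed |
| Investigator SAE report (Protocol 7.2.1.4) | none | none needed |

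**5. Size per affected patient.** The inputs are 500 randomized at 2:2:1 (Protocol synopsis) and the assumption that all are dosed.

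- Each ciprofloxacin-containing arm: 500 × 2/5 = 200. Fluocinolone arm: 500 × 1/5 = 100.
- One affected patient with no other SAE adds 1/n to the arm's SAE incidence: 1/200 = 0.5 percentage points, or 1/100 = 1.0 point.

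For scale only, the earlier trial had 1 SAE in 590 subjects, and 1/590 = 0.17%. The documents give no expected rate of missing severity, so the number of affected patients cannot be estimated.

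**The case against.** The strongest reply is that this is a one-word slip whose meaning is plain from context, and that the data controls leave it little to act on. Severity must be recorded (Protocol 7.2.1.2.2), entries are verified against source (Protocol 9.1), and missing data are taken up with the investigator and queried (Protocol 9.2). Expedited reporting follows the investigator's assessment, not a SAP imputation. SAP 4.7.1.2 rules out formal testing of safety results. All of this stands, and it limits the number of events affected. It does not make the sentence right, because a missing-data rule exists for the cases that queries fail to resolve.

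A reader might infer three stronger points that the documents do not support.

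- **That the sponsor means to count such events as SAEs.** The neighbouring items and the separate output rows point to a wording error.
- **That one such event would double the SAE count.** Going from s to s + 1 SAEs doubles the count only when s = 1. The ratio is 3/2 when s = 2, and there is nothing to double when s = 0. Taking s near 1 means carrying the earlier trial's rate over: 500 × 1/590 = 0.85. That trial enrolled from age 7, dosed three times daily for 8 days and had ciprofloxacin in both arms. This one enrolls from 6 months, doses twice daily for 7 days and has an arm without an antibiotic.
- **That the SAE tables would contradict the SAE listing.** Item 8 is a general rule and is not confined to tables. Read literally, it could put the event in both. Only the mismatch with the recorded seriousness data and with investigator SAE reports follows from the text.

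Counting missing severity as severe is also only one convention. A separate missing category in the severity tables would be defensible too. Item 5 is the reason to prefer the worst case here.

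**Conclusion.** Wrong as written. Item 8 assigns a missing severity to seriousness, apparently in error for *severe*, and nothing else in the documents corrects it. Followed literally, it inflates the SAE tables and leaves the severity tables incomplete.

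The practical size is small. It requires an event whose severity is still blank at database lock and a program that follows the sentence literally. The per-patient increments, 0.5 or 1.0 percentage points by arm, rest on full dosing at 200:200:100 and on the patient having no other SAE. No efficacy conclusion, error rate or clinical management rule is touched. The correction is still worth making, because SAE tables are read closely and the change is trivial.

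**What to change.** Replace item 8 of SAP 4.8.2 with:

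> If severity is missing, the event will be counted as severe in the summaries by severity and shown as missing in the listings; seriousness is taken only from the recorded seriousness field.

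This uses the same-scale worst case of item 5, gives the severity tables a category for every event, and leaves SAE counts as recorded. The cost is one sentence in the SAP before database lock, plus a check that the table shells and programming specifications say the same.

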4.8.3 Deaths, Serious Adverse Events, and Other Significant Adverse Events

An overview of AEs, including the number and percentage of patients who died, reported SAEs, and discontinued due to AEs will be provided. The incidence of treatment emergent SAEs will be presented by SOC, PT, and treatment group.

Listings of all SAEs and deaths as well as AEs leading to discontinuation will be provided.

4.8.4 Vital Signs, Physical Findings and Other Observations Related to Safety

4.8.4.1 Vital Signs

Summaries of blood pressure (systolic and diastolic), temperature, and heart rate will be presented by visit and treatment group. Summary statistics will be produced for both observed and change values from baseline for each parameter.

If there are multiple records of vital sign measurements at a visit, the last record will be used.

Unscheduled visits and repeat measurements will be excluded from the summaries, but included in listings. Missing data will be maintained as missing.

4.8.4.2 Physical Examination

Physical examination abnormalities at Visit 1 will be listed.

4.8.4.3 Pregnancy Test

Pregnancy Test results at Visit 1 for female patients of childbearing potential will be listed.

4.9 Antimicrobial Susceptibility

The number of pathogens isolated along with the Minimal Inhibitory Concentration required to inhibit the growth of the bacteria tested (MIC) will be summarized by treatment group at Visit 3 (EOT) and Visit 4 (TOC) for each bacterial species identified as “target OTIC organism” (*P. aeruginosa* and *S. aureus*).

Antimicrobial susceptibility against Ciprofloxacin and other antibiotics tested (as shown in Table 4-1) was presented as follows:

Table 4-1 Antibiotics tested for susceptibility results by organism

Drug	Organism	
	S. aureus	P. aeruginosa
Ciprofloxacin	✓	✓
Ofloxacin	✓	✓
Azithromycin	✓	
Amoxicillin	✓	
Amoxicillin/Clavunate	✓	
Cefuroxime	✓	
Trimethoprim/Sulfamethoxazole	✓	✓
Methicillin	✓	

4.10 Determination of Sample Size

Planned enrollment is 500 children, adolescents and adults. Patients will be stratified at enrollment so that approximately 50% of those enrolled will be younger than 18 years old and approximately 50% will be over 18 years old or older. Stratification is being performed to ensure adequate representation of each age group in the study and not for statistical considerations.

We have not been able to find an accurate estimation of study's main variable (therapeutic cure) in previous investigations with Ciprofloxacin 0.3% otic solutions in the treatment of AOE. Rates of patients cured, with different definitions from ours, have been estimated within a range between 60% and 70%. Moreover, in two comparative trials testing the same combination (same product) versus Ciprofloxacin alone in the treatment of AOMT, the percentage of therapeutic cure in patients with *Pseudomonas aeruginosa* and *Staphylococcus aureus* was around 50%.

For the calculation of the sample size for this study, the assumption is made that the Ciprofloxacin alone group will have a therapeutic cure rate of 62%, and that the combination will increase it by a relative 25%, which would represent a therapeutic cure rate of 78%. Assuming a two-sided significance level of 5%, and a statistical power of 80%, the required number of patients in each group would be 150. The randomization schedule is defined as 2:2:1 (Ciprofloxacin plus Fluocinolone

acetonide:Ciprofloxacin:Fluocinolone acetonide), so the total number of evaluable patients to be recruited is 375 (150 : 150 : 75). It is expected that approximately 80% of enrolled patients will complete the study.

In this study, evaluable patients are those with a positive pathogen microbiological culture at baseline (MITT population). From previous studies in AOE, the rate of patients included with a negative culture at baseline is approximately 25%, and therefore the number of patients to be finally recruited to obtain 375 evaluable patients would be 500.

4.11 Changes in the Conduct of the Study or Planned Analysis

Changes in the conduct of the study may be instituted through a protocol amendment. Planned analyses will be revised as appropriate. Changes will be finalized prior to database lock.

Appendix 1 Schedule of Observations

Table 2 Schedule of Observations

Evaluation	Visit 1 Screening/ Study Entry	Visit 2 By Telephone	Visit 3 End of Treatment	Visit 4 Post- Treatment Follow-Up
Study Day	1	3-4	8-10 or within 2 days of early termination	15-17
Informed Consent (and Assent Form when applicable)	X			
Inclusion/exclusion criteria	X			
Medical history	X			
Concurrent symptoms/conditions	X			
Urine pregnancy test ^a	X			
Physical examination	X			
Vital signs ^b	X		X	X
Brighton grading	X		X	X
Ear pain	X		X	X
Edema	X		X	X
Ototorhea	X		X	X
Overall Clinical Outcome			X	X
Microbiological culture of ear discharge ^c	X		X	X
Register patient visit through IWRS	X	X	X	X
Randomization through IWRS	X			
Dispense study medication and explain its use	X	X ^d		
Collect used and unused study medication containers			X ^e	
Dispense patient diary and explain its use	X			
Inquire about otitis symptoms		X ^f		
Review patient diary			X	X
Concomitant medications	X	X	X	X
Adverse events	X	X	X	X

^a For female patients of childbearing potential.

^b To include temperature, blood pressure, and pulse rate.

^c If no discharge is present, no attempt to culture will be made.

^d If patient with unilateral AOE at baseline becomes bilateral prior to Visit 3 a resupply study medication kit (with the same medication) will be dispensed^e

If patients forget to bring in containers at Visit 3, they must bring them in no later than Visit 4.

^e If patients report no improvement in otitis symptoms, they will be asked to come in for a visit as soon as possible. At this visit, they may prematurely discontinue study treatment (in which case the visit will be recorded as Visit 3, the End of Treatment visit) or continue study treatment (in which case the visit will be recorded as an unscheduled visit).
